## **9.7 STATISTICAL METHODS**

All statistical analyses will be performed by the sponsor or designee after the study is completed and the database is locked and released for unblinding. However, unblinded safety analyses for review by a DSMB will be conducted by an independent statistical group prior to database lock. Statistical analyses will be performed using SAS® software or other validated statistical software

as required. Details of the planned statistical analyses are outlined below; further details will be included in a separate statistical analysis plan (SAP).

### 9.7.1 Statistical and Analytical Plans

The statistical analyses of study data are described in this section. Further details of the analytical plan will be provided in the SAP, which will be finalized before the unblinded interim safety analyses, final database lock and treatment unblinding, and will be included in the clinical study report. An interim statistical analysis plan, describing the safety analyses planned for the purposes of review by the DSMB, will also be produced.

#### 9.7.1.1 Study Endpoints

##### PRIMARY ENDPOINTS

The primary efficacy endpoint is the proportion of subjects who do not require a platelet transfusion or any rescue procedure for bleeding after randomization and up to 7 days following an elective procedure.

##### SECONDARY ENDPOINTS

The secondary efficacy endpoints are:

- Proportion of responders defined as subjects who achieve platelet counts of  $\geq 50 \times 10^9/L$  on Procedure Day (ie, prior to receiving a platelet transfusion or undergoing the elective procedure)
- Change from baseline in platelet count on Procedure Day (ie, prior to receiving a platelet transfusion or undergoing the elective procedure)

(revised per Amendment 04)

##### EXPLORATORY ENDPOINTS

The exploratory endpoints are:

- Platelet count and change from baseline in platelet count at each visit
- Proportion of subjects who achieve platelet count of  $\geq 50 \times 10^9/L$ ,  $\geq 75 \times 10^9/L$ , or  $\geq 200 \times 10^9/L$  at each visit
- Number of platelet units used per platelet transfusion episode
- Severity of bleeding events assessed by WHO bleeding score and BARC bleeding scale
- Proportion of subjects with a WHO bleeding score  $\geq 2$  after randomization and up to 7 days following an elective procedure (revised per Amendment 04)
- Health economics assessed by resource use

### 9.7.1.2 Definitions of Analysis Sets

Full Analysis Set (FAS): The FAS is the group of randomized subjects. The FAS will be analyzed “as randomized”.

Per Protocol Set (PP): The PP Set is the group of all randomized subjects who receive protocol-assigned study drug and do not meet any of the following criteria:

- Subjects who have any major protocol violations (major inclusion/exclusion violations or other major protocol violations that impact the evaluation of efficacy)
- Subjects who use a prohibited concomitant medication that affects the assessment of study endpoints
- Subjects who are noncompliant in terms of study medication

A comprehensive list of subjects to be excluded from the PP will be agreed upon by the study team prior to database lock. The PP will be analyzed “as randomized”.

Safety Analysis Set: The Safety Analysis Set is the group of subjects who receive at least 1 dose of study drug and have at least 1 postdose safety assessment. This set will be analyzed “as treated.”

PK Analysis Set: The PK Analysis Set is the group of randomized subjects who receive at least 1 dose of avatrombopag and have at least 1 quantifiable avatrombopag concentration with a documented dosing history.

PK/PD Analysis Set: The PK/PD Analysis Set is the group of randomized subjects who receive at least 1 dose of avatrombopag, have at least 1 quantifiable avatrombopag concentration, and at least 1 platelet count, with a documented dosing history.

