### **Analysis Sets**

Full Analysis Set (FAS): The FAS is the group of randomized subjects. The FAS will be analyzed “as randomized”.

Per Protocol Set (PP): The PP Set is the group of all randomized subjects who receive protocol-assigned study drug and do not meet any of the following criteria:

- Subjects who have any major protocol violations (major inclusion/exclusion violations or other major protocol violations that impact the evaluation of efficacy)
- Subjects who use a prohibited concomitant medication that affects the assessment of study endpoints
- Subjects who are noncompliant in terms of study medication

A comprehensive list of subjects to be excluded from the PP will be agreed upon by the study team prior to database lock.

Safety Analysis Set: The Safety Analysis Set is the group of subjects who receive at least 1 dose of study drug and have at least 1 postdose safety assessment. This set will be analyzed “as treated.”

PK Analysis Set: The PK Analysis Set is the group of randomized subjects who receive at least 1 dose of avatrombopag and have at least 1 quantifiable avatrombopag concentration with a documented dosing history.

PK/PD Analysis Set: The PK/PD Analysis Set is the group of randomized subjects who receive at least 1 dose of avatrombopag, have at least 1 quantifiable avatrombopag concentration, and at least 1 platelet count, with a documented dosing history.

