### 8.3 EXPLORATORY OBJECTIVES

The exploratory objectives of the study are:

- To characterize the pharmacokinetics and the relationship between avatrombopag plasma concentrations and platelet count using the population approach
- To characterize platelet count changes from baseline, the extent of platelet transfusion use, evaluate the incidence of bleeding events, and assess the severity of any bleeding events (revised per Amendment 04)
- To assess the health economic impact associated with minimizing the need for platelet transfusions and any rescue procedure for bleeding associated with an elective procedure

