#### 9.1.1.1 Screening Period (Visit 1)

Screening will occur between Day -14 and Day -1.

The purpose of the Screening Period is to obtain informed consent and to establish protocol eligibility. Subjects must have a diagnosis of thrombocytopenia associated with liver disease and be scheduled to undergo an elective procedure. Only subjects who, in the opinion of the investigator, are expected to require platelet transfusion to address a risk of bleeding associated with the procedure will be recruited into this study.

Informed consent will be obtained after the study has been fully explained to each subject and before the conduct of any screening procedures or assessments. Procedures to be followed when obtaining informed consent are detailed in [Section 5.3](#).

After providing informed consent, all subjects will undergo screening assessments to ensure that they meet all of the inclusion and none of the exclusion criteria, as described in [Section 9.3.1](#) and [Section 9.3.2](#). Screening assessments and timing are shown in [Section 9.5.2.1 \(Table 5\)](#).

During this phase, the type and schedule of the elective procedure will be confirmed.

The Screening Disposition case report form (CRF) page must be completed to indicate whether the subject is eligible to participate in the study and to provide reasons for screen failure, if applicable.

Rescreen of subjects will only be allowed under the following circumstances:

- Scheduled procedure is cancelled or delayed
- Platelet count inclusion criteria is not met as platelet count tends to fluctuate
- Unable to complete the Screening Period due to administrative, logistical issues
- Previously screen failed due to criteria no longer in the protocol (added per Amendment 01)

Repeat of screening laboratory evaluations are allowed in cases where abnormal result(s) are noted during the Screening Period that are believed to be related to a potential laboratory error or a transient and/or reversible condition (eg, clumped platelets or hemolyzed sample for complete blood count). Results of the repeated assessment must be available before randomization. If additional blood samples are sent to the central laboratory during the Screening Period, eligibility must be assessed based on the most recent laboratory values. The 2 most recent values will be used to determine the mean platelet count value for entry criteria and for assignment to the low or high baseline platelet count cohort.

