#### **PHARMACOKINETIC/PHARMACODYNAMIC ANALYSES**

The relationship between avatrombopag concentration and platelet count will be analyzed using a population PK/PD approach to estimate population PD parameters and the effect of covariates on the PD parameters will be evaluated.

For the PK/PD modeling, data from this study will be pooled with PK/PD data from two Phase 2 studies in subjects with thrombocytopenia associated with liver disease, including hepatitis C, and possibly with data from Phase 1 studies.

The population PK and PK/PD analyses will be detailed in a separate analysis plan.

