5.5 PHARMACOKINETIC , PHARMACODYNAMIC, AND PHARMACOGENOMIC/PHARMACOGENETIC ANALYSES

Population pharmacokinetic (PK) and pharmacokinetic/pharmacodynamic (PK/PD) analysis are specified in the protocol but will not be discussed in this SAP. Separate analysis plan(s) for these analyses will be developed and finalized before the database lock.

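### The PK/PD Analysis Set excludes all of this study's placebo subjects, so the exploratory concentration–platelet model has no concurrent untreated data from this trial

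*Protocol*

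**What the plan says.** Protocol 8.3 lists as an exploratory objective: "To characterize the pharmacokinetics and the relationship between avatrombopag plasma concentrations and platelet count using the population approach". Protocol 9.7.1.7 repeats the aim: "The relationship between avatrombopag concentration and platelet count will be analyzed using a population PK/PD approach". It adds that covariate effects on the PD parameters will be evaluated.

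The set for this work is defined in Protocol 9.7.1.2 thus: "group of randomized subjects who receive at least 1 dose of avatrombopag, have at least 1 quantifiable avatrombopag concentration, and at least 1 platelet count"; dosing must also be documented. The synopsis has the same rule: "The PK/PD Analysis Set is the group of randomized subjects who receive at least 1 dose of avatrombopag". SAP 5.2.1 defines the FAS, PP and Safety sets but no PK/PD set.

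The model itself is not in either document. Protocol 9.7.1.7 says "The population PK and PK/PD analyses will be detailed in a separate analysis plan", and SAP 5.5 says "Separate analysis plan(s) for these analyses will be developed and finalized before the database lock". Protocol 9.7.1.7 also says that "data from this study will be pooled with PK/PD data from two Phase 2 studies", and possibly with Phase 1 data. It does not say whether placebo records from those studies are kept.

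On selection, entry requires a mean of two counts below 50 × 10⁹/L with neither above 60. Protocol 9.1.1.1 allows rescreening on this ground: "Platelet count inclusion criteria is not met as platelet count tends to fluctuate".

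**The concern.** A concentration–response model needs to know what happens to platelet counts when there is no drug. Here every treated subject is dosed on Days 1 to 5 and counted on nearly the same days, so drug effect and any untreated change since baseline run on the same clock. Subjects are admitted because their counts are low, and counts fluctuate, so some upward movement without drug is plausible. The placebo arms are the direct concurrent control for it, and the set definition shuts them out.

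The dose structure adds to this. The 60 mg dose is given only below 40 × 10⁹/L and the 40 mg dose only from 40 to <50 × 10⁹/L. If untreated change differs between the cohorts, the difference could resemble a covariate effect of baseline count. Each cohort has its own placebo arm, and the set uses neither. What is at stake is the reliability of an exploratory drug-effect and covariate analysis.

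**Working it through.** The documents state no figure for the PK/PD set, so there is none to reproduce. The arm sizes come from Protocol 9.7.2, whose power claim does reproduce: 67 v 33 per cohort, 53% v 18%, Fisher's exact test, two-sided 0.05, gives 92.6% by exact enumeration against the stated figure of more than 90%. The point does not depend on it.

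**1. Who is left out.** Planned arms are 133 avatrombopag and 67 placebo (Protocol 9.7.2).
- Placebo share: 67/200 = 33.5%.
- Largest planned PK/PD set as defined: 133. With placebo admitted: 133 + 67 = 200.
- Avatrombopag subjects without a quantifiable level are also excluded. The documents give no number. With three samples and a 1.00 ng/mL limit (Protocol 9.5.1.4) they are probably few.

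**2. Which placebo counts would be useful.** Table 5 schedules local-laboratory platelet counts at Visits 3, 4, 5 and 6.
- All four visits: 67 × 4 = 268.
- Visits 5 and 6 come after the procedure: 67 × 2 = 134. The protocol assumes an 18% placebo response, so 67 × (1 − 0.18) = 54.9, about 55 subjects, would be non-responders, mostly through transfusion or rescue. Many of these later counts would not represent untreated change.
- Visits 3 and 4: 67 × 2 = 134. A Table 5 footnote requires hematology to be drawn before any platelet transfusion.
- The pharmacodynamic text in Protocol 9.5.1.4 omits Visit 3. On that text alone only Visit 4 remains, 67 × 1 = 67. So 134 is an upper figure that rests on Table 5.

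**3. Is change without drug plausible?** Protocol 7.1.2.3 reports that in the Phase 2 liver-disease study 8.1% of placebo subjects met the responder definition (a rise of at least 20 and a count of at least 50 × 10⁹/L), against 48.4% on drug. The difference is 48.4 − 8.1 = 40.3 points, and 8.1/48.4 = 0.17. This mixes drift with random fluctuation, so it shows that counts move without drug but does not measure a mean drift.

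**4. How large could regression to the mean be?** This is illustration only. The documents give no between-subject SD (sb), within-subject SD (sw) or population mean, so all of these are assumed.
- Fraction of the distance to the population mean regained by a mean of two counts: (sw²/2)/(sb² + sw²/2).
- sb 15, sw 5: 12.5/(225 + 12.5) = 0.053. sb 10, sw 10: 50/(100 + 50) = 0.333.
- With an assumed distance of 10 to 15: 0.053 × 10 = 0.5 up to 0.333 × 15 = 5.0 × 10⁹/L.
- A simulation applied the entry rule, with population mean/SD of 45/12, 55/15 or 70/25 and within-subject SD of 3, 6 or 10. Mean untreated change was about +0.3 to +4.3 in the <40 cohort and 0 to +1.8 in the 40 to <50 cohort (× 10⁹/L).

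**5. What cannot be computed.** Turning such a change into bias in a PD parameter needs the model's structure and its pooled data. Neither is in the documents.

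**The case against.** A reader might infer that the trial throws away its placebo platelet counts. It does not. Counts are measured in all subjects, and the FAS analyses use them: the CMH test of reaching 50 × 10⁹/L on Procedure Day (SAP 5.4.2.1), the Wilcoxon and Hodges-Lehmann comparison of change from baseline (SAP 5.4.2.2) and the by-visit comparisons (SAP 5.4.3.1). A placebo-controlled estimate of the platelet effect is already planned.

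A reader might also infer that the model will credit untreated drift to the drug. A set definition cannot establish that. The separate plan may contain baseline or drift terms, and the Phase 2 study described in Protocol 7.1.2.3 had placebo arms whose records may be pooled. Treated subjects also supply two entry counts and a Day 35 count, 30 days after the last dose, so some off-drug information remains in the set.

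Nor do these documents make this set the basis for dosing by baseline count. The doses were chosen from modelling of the earlier Phase 2 study (Protocol 7.1, 7.2, 9.4.4) and are fixed here.

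All of this stands, and it limits the point to an exploratory analysis with a harm of unknown size. It does not remove the point. The rule as written excludes this study's placebo subjects, and nothing in the pooling text says that any placebo record is kept.

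**Conclusion.** The PK/PD set, followed as written, excludes all 67 planned placebo subjects of 200 (33.5%) and leaves the model without this trial's concurrent zero-concentration data. That rests on the definition alone. That untreated change is plausible rests on the entry rule and the Phase 2 placebo response of 8.1%. Its size is not known: the drift figures depend wholly on assumed SDs and population means, and the bias in any PD parameter cannot be computed without the separate plan. No primary or secondary inference is affected. It is a modest point on an exploratory analysis, worth acting on because the data are already collected and the change is small.

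**What to change.** In Protocol 9.7.1.2 and the synopsis, define the PK/PD Analysis Set as randomized, dosed subjects with a documented dosing history and at least one platelet count. Then:

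- Enter placebo subjects at concentration zero.
- Keep avatrombopag subjects without a quantifiable level, under a stated rule for values below the limit of quantification.
- Use pre-transfusion counts (Visits 3 and 4), and exclude or model counts taken after a platelet transfusion.
- Leave the PK Analysis Set unchanged.
- Align the separate PK/PD plan, and have it state whether placebo records from the pooled studies are kept and how untreated change is represented. If that plan already includes placebo records, the protocol definition conflicts with it and the two need reconciling.

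Keeping the dosing-history requirement matters, because avatrombopag subjects without a measured level can enter a concentration–response model only through their dosing record. The cost is a change of wording before database lock, when the separate plan is due, and slightly more modelling work. No new data are needed.

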### 9.7.1.3 Subject Disposition

Subject disposition will be summarized by treatment group for the FAS and Safety Analysis set. The number (percentage) of subjects who completed or discontinued prematurely from the study and their reason for discontinuation will be summarized by treatment group. In addition, the number of subjects screened and the number and percentage of subjects who failed screening and the reasons for screen failure will be summarized, based on data recorded on the Screening Disposition CRF.

### 9.7.1.4 Demographic and Other Baseline Characteristics

Demographic and other baseline characteristics for the FAS and Safety Analysis set will be summarized for each treatment group using descriptive statistics or frequency count. Continuous demographic and baseline variables include age, weight, height, body mass index, MELD score, CTP score, and baseline platelet count; categorical variables include sex, race, ethnicity group, baseline platelet count stratification level, risk of bleeding associated with the elective procedure, and HCC status.

#### 9.7.1.5 Prior and Concomitant Therapy

All investigator terms for medications recorded in the CRF will be coded using the WHO Drug Dictionary. The number and percentage of subjects who took prior and concomitant medications will be summarized for the Safety Analysis set by treatment group, Anatomical Therapeutic Chemical class (indicating therapeutic class) and WHO Drug Dictionary preferred term. Prior medications will be defined as medications that stopped before the first dose of study drug. Concomitant medications will be defined as medications that (1) started before the first dose of study drug and were continuing at the time of the first dose of study drug, or (2) started on or after the date of the first dose of study drug up to 30 days after the subject's last dose.

#### 9.7.1.6 Efficacy Analyses

The FAS will be used as the primary population for the efficacy analyses, while the PP will be used as a supportive analysis. All analyses of platelet counts will be based on local laboratory results.

### PRIMARY EFFICACY ANALYSIS

The primary efficacy variable is the proportion of subjects who do not require a platelet transfusion or any rescue procedure for bleeding after randomization and up to 7 days following an elective procedure.

The null hypothesis is that the proportion of subjects not requiring a platelet transfusion or any rescue procedure for bleeding after randomization and up to 7 days following an elective procedure is the same between the avatrombopag and placebo treatment groups. The corresponding alternative hypothesis is that the proportion of subjects not requiring a platelet transfusion or any rescue procedure for bleeding after randomization and up to 7 days following an elective procedure is not the same between avatrombopag and placebo. This hypothesis will be tested separately within each baseline platelet cohort.

The proportion of subjects not requiring a platelet transfusion or any rescue procedure for bleeding will be tested between the individual avatrombopag treatment group (40 or 60 mg) and matching placebo within each baseline platelet count cohort ( $<40 \times 10^9/L$  or from 40 to  $<50 \times 10^9/L$ ), each at a significance level of  $\alpha=0.05$ , using the generalized Cochran Mantel Haenszel (CMH) test adjusting for risk of bleeding associated with the elective procedure (low, moderate, or high based on Amendment 02 categorization).

- For subjects with platelet count  $<40 \times 10^9/L$  at baseline, the treatment comparison will be carried out between the 60 mg avatrombopag treatment group versus matching placebo.
- For subjects with platelet count from 40 to  $<50 \times 10^9/L$  at baseline, the treatment comparison will be carried out between the 40 mg avatrombopag treatment group versus matching placebo.

This study will be considered as positive if statistical significance is achieved for the primary efficacy endpoint for both baseline platelet count cohorts.

The 95% confidence interval (CI) for the proportion of subjects not requiring a platelet transfusion or any rescue procedure for bleeding will be calculated for each treatment group within each baseline platelet count cohort. In addition, the 95% CI for the difference between avatrombopag and matching placebo will be provided within each baseline platelet count cohort.

Since the HCC status is included in the randomization stratification for safety purposes only, not for efficacy consideration, HCC will not be included in the CMH model for the primary efficacy analysis.

Subjects with missing information about the primary efficacy outcome due to early withdrawal or other reasons will be considered as having received a transfusion for the primary analysis.

The following analyses will be considered as sensitivity analyses:

- PP analysis: The same primary efficacy analyses described above will be repeated based on the PP analysis set.
- Observed case: The same primary efficacy analyses described above will be repeated based on observed data. Subjects with missing information about the primary efficacy outcome will be excluded from this analysis.
- Fisher's exact Test: The same primary efficacy analyses described above will be carried out using Fisher's exact test.
- Modified primary efficacy endpoint: Proportion of subjects who do not require a platelet transfusion after randomization and up to 7 days following an elective procedure. This efficacy endpoint will be analyzed using the same approach as primary efficacy analysis using FAS.

Additional sensitivity analyses may also be explored, if deemed appropriate.

## SECONDARY EFFICACY ANALYSES

There are 2 secondary efficacy endpoints in this study: (revised per Amendment 04)

- Proportion of responders defined as subjects who achieve target platelet counts of  $\geq 50 \times 10^9/L$  on Procedure Day (prior to receiving a platelet transfusion or undergoing the elective procedure)
- Change from baseline in platelet count on Procedure Day (prior to receiving a platelet transfusion or undergoing the elective procedure)

The analysis of the secondary efficacy variables as defined above will proceed following a sequential gatekeeping testing procedure with the multiplicity adjustment to control the Type I error rate at significance level  $\alpha=0.05$ .

The proportion of subjects who achieve platelet counts of  $\geq 50 \times 10^9/L$  on the Procedure Day will be analyzed first. The proportion of subjects with platelet counts of  $\geq 50 \times 10^9/L$  on the Procedure Day will be tested between the individual avatrombopag treatment group (40 or 60 mg) and matching placebo separately within each baseline platelet count cohort ( $< 40 \times 10^9/L$  or from 40 to  $< 50 \times 10^9/L$ ), each at a significance level of  $\alpha=0.05$ , using the generalized CMH test adjusting for risk of bleeding associated with the elective procedure (low, moderate, or high based on Amendment 02 categorization).

The second secondary efficacy variable, change from baseline in platelet count on the Procedure Day, will be analyzed only if the test for the first secondary efficacy variable is statistically significant for both baseline platelet count cohorts. The change from baseline in platelet count will be analyzed using the Wilcoxon rank sum test separately within each baseline platelet count cohort ( $< 40 \times 10^9/L$  or from 40 to  $< 50 \times 10^9/L$ ), each at a significance level of  $\alpha=0.05$ . (revised per Amendment 04)

